**Study Population, Eligibility, Setting, and Recruitment.** Forty healthy adults will be recruited and randomized to receive either 300 mg of CBD (N=20) or placebo (N=20). The criteria for eligibility are as follows: 1) the participant must be currently enrolled as a WVU student, 2) be 18-30 years of age at time of study, 3) have a current drivers' license issued from any state in the United States, 4) has driven at least once in the past 30 days 5) is able to speak and read English, 6) is willing to be randomized and comply with study requirements including a urine drug test on the day they consent to participate in the experiment and complete a test drive to ensure the absence of simulation sickness, 7) not currently taking any daily prescription medications other than birth control, 8) have not been diagnosed with any serious chronic disease by a licensed healthcare provider (including but not limited to Alzheimer's and related dementias, Parkinson's disease or other neurodegenerative disorder, major depressive or anxiety disorder, schizophrenia or other serious mental illness, arrhythmias, cataracts, glaucoma, chronic obstructive pulmonary disease, diabetes, epilepsy, sleep apnea, and fibromyalgia), and 9) has an individual able to drive them home after testing or is willing to be driven home by study staff after testing completion.

Participants will be excluded if they 1) currently smoke or use tobacco products, 2) have used illegal drugs (including cocaine/crack, heroin, methamphetamine, 3,4-methylenedioxy-methamphetamine, inhalants, phencyclidine, lysergic acid, mushrooms, or marijuana) in the past 30 days, 3) has consumed CBD in the past 7 days, or 4) is currently pregnant or lactating. The health conditions and substances noted above have all been associated with changes in driving ability or performance. Also, limiting participants to those who are currently not using illegal drugs, tobacco products, and prescription medications may help minimize bias potentially caused by drug interactions with CBD or known impediments to driving performance from the medications themselves. Participants will be recruited from WVU. Email notifications about the study will be sent to the student body and flyers will be posted on boards throughout campus; this type of recruitment has been successful in other studies. The study will take place at the WVU Health Sciences Center.

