### Target Population & Recruitment Methods

Our sample size is 40 individuals. We chose this number based on an a priori power analysis.

Our inclusion and exclusions criteria are as follows: 1) the participant must be currently enrolled as a WVU student, 2) be 18-30 years of age at time of study, 3) have a current drivers' license issued from any state in the United States, 4) has driven at least once in the past 30 days 5) is able to speak and read English, 6) is willing to be randomized and comply with study requirements including a urine drug test on the day they consent to participate in the experiment and complete a test drive to ensure the absence of simulation sickness, 7) not currently taking any daily prescription medications other than birth control, 8) have not been diagnosed with any serious chronic disease by a licensed healthcare provider (including but not limited to Alzheimer's and related dementias, Parkinson's disease or other neurodegenerative disorder, major depressive or anxiety disorder, schizophrenia or other serious mental illness, arrhythmias, cataracts, glaucoma, chronic obstructive pulmonary disease, diabetes, epilepsy, sleep apnea, and fibromyalgia), and 9) has an individual able to drive them home after testing or is willing to be driven home by study staff after testing completion.

Participants will be excluded if they 1) currently smoke or use tobacco products, 2) have used illegal drugs (including cocaine/crack, heroin, methamphetamine, 3,4-methylenedioxy-methamphetamine, inhalants, phencyclidine, lysergic acid, mushrooms, or marijuana) in the past 30 days, 3) has consumed CBD in the past 7 days, or 4) is currently pregnant or lactating. The health conditions and substances noted above have all been associated with changes in driving ability or performance. Also, limiting participants to those who are currently not using illegal drugs, tobacco products, and prescription medications may help minimize bias potentially caused by drug interactions with CBD or known impediments to driving performance from the medications themselves.

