**Sample Size** – We conducted an analysis to ensure adequate sample size and power. The analysis was based on mean reaction time, which is one of the primary outcomes between groups. A total sample size of 26 students with a large effect size of 0.7 and  $\alpha=0.05$  using a two-sided, two-sample equal variance t-test achieves 80% power to reject the null hypothesis of equal means. Thus, our total sample size (N=40) should be more than adequate for this study.

**Data Safety Monitoring** – A Data Safety Monitoring Board will not be appointed for this study unless required.

 Table 2. Overview of proposed variables to be collected and for CBD studya

Aim	Variables	Source
	Socio-demographics, driving history, health	Baseline questionnaire
Aim 1. Determine the effects of CBD on the driving performance of healthy adults aged 18-30 years.	Driving performance 
 
Number of lane departures
 
Number of collisions
 
Mean brake reaction time to stimuli
 
Mean standard deviation of lateral position in lane under consistent speed
 
	Driving simulation
Aim 2. Determine the effects of CBD on participants psychological status and cognitive function.	Sedation 
 
Self-reported sleepiness
 
Mental sedation: Sum of scores from questions 1,4,11,13 on VAMS—higher scores indicate more mental sedation
 
Physical sedation: Sum of scores from questions 3,5,6,16 on VAMS—higher scores indicate more physical sedation
 
 Cognitive function 
 
Number of symbols completed within 60 seconds
 
Number of correct symbols completed within 60 seconds
 
Time to accurately complete Part A and Part B
 
Mean reaction time to stimuli
 
Mean reaction time to stimuli
 
	SSS VAMS VAMS DSST TMT PVT SRT
Aim 3. Determine the relation of driving performance to changes in psychological and cognitive status.	Correlation between variables in Aims 1 and 2	Driving simulation outcomes, SSS, VAMS, DSST, TMT, PVT, SRT

a: All measures will be assessed between treatment and placebo groups. DSST, SSS, TMT, PVT, SRT and VAMS scores will also be compared within subjects to gauge changes overtime.

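### The stated 80% power is wrong: 26 students in total give about 40% at an effect size of 0.7, and the planned 40 give about 58%

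*Combined protocol and SAP*

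**What the plan says.** The Sample Size paragraph of the Statistical Analysis Plan bases the calculation on a single outcome: "The analysis was based on mean reaction time, which is one of the primary outcomes between groups". It then states: "A total sample size of 26 students with a large effect size of 0.7" at alpha 0.05, with a two-sided, "two-sample equal variance t-test achieves 80% power to reject the null hypothesis of equal means". From this it concludes: "Thus, our total sample size (N=40) should be more than adequate for this study".

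The Target Population & Recruitment Methods section relies on the same calculation to justify 40 participants: "We chose this number based on an a priori power analysis". No other power analysis appears in the document. Study Design & Methodology fixes the allocation at 1:1, with 20 on CBD and 20 on placebo. No raw difference, standard deviation, source for the 0.7, or dropout rate is given.

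**The concern.** A total of 26 looks far too small for a two-sided comparison of two independent groups at 0.7 SD. If the figure is wrong, the 14 participants above 26 are not a safety margin, and 40 falls short of the power the plan claims.

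What is at stake is how the result will be read. The question is one of driving safety, and the Significance section looks ahead to public health, education and legislative uses of the findings. The Background attributes earlier non-significant CBD results to very small samples. A reader told that this trial was more than adequately powered could take a non-significant difference as evidence that CBD does not impair driving, when the trial may simply have been too small to show it.

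**Working it through.** **Inputs.** Effect size d = 0.7, read as a standardised mean difference because the plan names a two-sample t-test; alpha = 0.05, two-sided; equal variances; stated total 26 (all from the Sample Size paragraph). Allocation is 1:1 (Allocation, Randomization and Blinding), so 26 in total is 13 per arm. The planned arms are 20 and 20. No loss is assumed, since the plan gives no dropout rate and intends to impute missing data.

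**Formula.** With n per arm, the t statistic under the alternative is noncentral t with 2n − 2 degrees of freedom and noncentrality d·√(n/2). Power is the probability that it exceeds the two-sided 5% critical value in absolute size.

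**The plan's own figure: 13 per arm.** Noncentrality 0.7 × √6.5 = 1.785; 24 df; critical value 2.064. Power = **40.3%**, against the stated 80%. A simulation of 100,000 trials gives 40.6%.

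**The planned trial: 20 per arm.** Noncentrality 0.7 × √10 = 2.214; 38 df; critical value 2.024. Power = **57.8%** (simulation 57.9%). The chance of missing a true 0.7 SD difference is 100 − 57.8 = 42.2%.

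**What 80% would need at d = 0.7.** The solution is 33.02 per arm. Power at 33 per arm is 79.97% and at 34 per arm 81.2%, hence 34 per arm and 2 × 34 = 68 in total, which is 28 more than planned.

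**What 20 per arm can do.** Power of 80% is reached at d = 0.909, about 0.91. The 95% confidence interval for a mean difference has half-width 2.024 × √(2/20) = 0.64 SD.

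**Can another reading recover 26 at 80%?**

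| Reading, effect size 0.7 | Power |
|---|---|
| Two-sided, 13 per arm (as printed) | 40.3% |
| One-sided, 13 per arm | 53.6% |
| Two-sided, 26 per arm | 69.7% |
| One-sided, 26 per arm | 80.1% |
| Paired test, 26 pairs | 92.9% |
| 0.7 taken as Cohen's f (d = 1.4), 13 per arm | 92.8% |

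Of these, only a one-sided test with 26 in each arm gives 80% (it solves to 25.94 per arm). That contradicts the text on both sidedness and the word total. Even then 52 participants would be needed, and 40 would give 70.2%.

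**The case against.** Nobody disputes the arithmetic on the printed inputs. The strongest reply is that the faulty input may be the effect size. At d = 1.15, 13 per arm does give 80.3% power two-sided; every other term in the sentence would then be right, and 40 participants would have 94% power for that effect. This needs one slip, whereas the one-sided, per-group explanation needs two. It is a fair caution about cause: the documents cannot show how 26 arose, and neither explanation can be confirmed. It does not rescue the statement, because the plan prints 0.7, and at 0.7 the power is not 80%.

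A second reply is that the trial calls itself exploratory and describes its product as preliminary data, lists four driving measures as primary, and makes no claim of non-inferiority. Missing an effect on one measure would therefore not by itself make the whole trial a null result. That stands, and the exploratory aim may justify 40 participants on other grounds. It does not make a false power figure true.

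A third reply is that confidence intervals and a sentence on interpretation go beyond correcting an arithmetic error. That is so. They are included because the correction leaves the power low, and they protect the reading of the result at almost no cost.

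**Conclusion.** The concern holds. On the plan's own inputs, 26 students in total give 40.3% power, about half the stated 80%, and the planned 40 give 57.8%. The claim that 40 is more than adequate is not supported at an effect size of 0.7.

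The result rests on reading 0.7 as a standardised mean difference, equal arms, normally distributed outcomes, and no loss of participants. It applies to one reaction-time outcome tested at the full 0.05. With four driving measures named as primary, an illustrative Bonferroni split to 0.0125 would lower the power at 20 per arm to about 35%, so 58% is not a pessimistic figure. How the error arose is unknown, and the conclusion does not depend on it. This must be corrected because it is the only stated basis for the sample size.

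**What to change.** Keep 40 participants and correct the text. In the Sample Size paragraph, delete the sentence on 26 students and the claim of adequacy, and replace them with wording such as:

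> With 20 participants per group, a two-sided two-sample t-test at alpha = 0.05 has 58% power for a standardised difference of 0.7 and 80% power for a difference of 0.91. Power of 80% at 0.7 would need 34 per group. These figures apply to a single outcome, without adjustment for multiple primary measures and without loss of participants.

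This wording is true whichever input was at fault. If the intended effect size was not 0.7, the sponsor should say so and justify the value used.

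Add that each driving outcome will be reported as a between-group difference with a 95% confidence interval, and that a non-significant result will not be taken to show absence of impairment. Align the sentence in Target Population & Recruitment Methods that attributes the number 40 to a power analysis.

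The cost is an edit to the protocol and SAP text and a less favourable power statement. Enrolment does not change. If the sponsor wants 80% power at 0.7, the alternative is 68 participants, 28 more than planned.

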### **Study Duration & Timeline**

The projected timeline of this study is below. It should take 24 months to complete.

C5.14. Projected Timeline (task and months to complete)	1	2	3	4	5	6	7	8	9	10	11	12	13	14	15	16	17	18	19	20	21	22	23	24
1. Recruitment	X	X																						
2. Conduct testing		X	X	X	X	X	X	X	X	X	X	X	X	X	X	X	X	X						
3. Data management & analysis																			X	X	X	X		
4. Manuscript preparation																				X	X	X	X	
5. Dissemination																						X	X	

### **Section III: Informed Consent Process**

#### **Protected Health Information (PHI)**

There will be PHI collected from this study. This will mainly come from the consent process. We will obviously collect the person's name on the consent form. After this, they will be assigned a study identification number and everything else will be de-identified. We will ask if they have any chronic medical conditions or take medication or illegal drugs. If they do, they can't participate in the study.

#### **Informed Consent Process**

[name] or her designee will perform the written consent process, which will take place in her office which is private. The Informed Consent Form (ICF) will be written in lay terms and at a 6th grade reading level. All study participants will be 18 or over so assent will not be necessary.

### Confidentiality & Privacy

**Confidentiality** – All data collected will be kept for a minimum of 3 years after the conclusion of the research project. Physical copies of data collected will be locked in a drawer or file cabinet, within the PI's locked office. Digital data will be stored on an encrypted, password protected database located on a secure server maintained by WVU IT Department. All participant identifiers will be stored separately from the data collected.

**Privacy** – Data will be stored securely to protect the privacy of participants. Only the minimum amount of data will be collected to ensure participant privacy. The driving simulation and neurocognitive tests will occur in a quiet, secured office to maintain privacy.

A **Federal Certificate of Confidentiality** will be obtained if necessary to further protect participants.

## Section IV: Other Considerations

### Conflict of Interest

The PI and Co-Investigators have no conflicts of interest.

### Publications, Presentations, & References

The PI will likely present the results of this study at one of the following conferences: Transportation Research Board, Society for the Advancement of Violence and Injury Prevention, American Public Health Association.

The PI will likely publish the results of this study in one of the following journals: American Journal of Epidemiology, Injury Prevention

